This amendment serves to clarify inconsistencies and to provide further guidance for trial assessments and procedures per clinical study protocol.

Section # and Name (page #)	Current Language	Proposed Language (New text will be bolded and deleted text will be struck through)	Rationale for Change
1.1 Synopsis (p.17)	Sixty (60) healthy older adult participants aged 55 to 75 years will be randomized in two cohorts; 30 obese and/or diabetic participants aged 55 to 75 years will be randomized in two cohorts.	Sixty (60) healthy older adult participants aged 55 to 75 years at screening will be randomized in two cohorts; 30 obese and/or diabetic participants aged 55 to 75 years at screening will be randomized in two cohorts.	Clarification that eligible age is considered at screening.
1.3 Schedule of Activities (p.21)	i Between Day 57 (28 days post second injection) to Day 168 and from 28 days after the third vaccine to Day 365 only MAAEs, AESIs and SAEs will be collected.	i Solicited AE/SAEs will be collected 7 days post each vaccination in the eDiary. j Between Day 57 58 (28 days post second 2nd injection) to Day 168 161 and from 28 days after the third 3rd vaccine to Day 365 only MAAEs, AESIs, and SAEs will be collected. k Between Day 1 to Day 57 and Day 162 to Day 197 all CMs will be collected. Between Day 58 to Day 161 and Day 198 to Visit 12 (Day 365): only CMs taken for MAAEs, AESIs, and SAEs, which are collected within this period will be recorded.	Table flow chart and table footnotes edited to provide clarity to collection of adverse events (AEs) and concomitant medications (CMs).
5.0 Study Population (p.30)	N/A	Data from screening procedures will be used for treatment allocation if a procedure is not planned or repeated at Visit 2. Procedures will not be repeated at Visit 4 and Visit 8.	Clarification how eligibility data should be handled if procedure is not repeated prior to 1 st dosing.

Section # and Name (page #)	Current Language	Proposed Language (New text will be bolded and deleted text will be struck through)	Rationale for Change
5.0 Study Population (p.30)	N/A	
 The investigator should consider whether a participant with BMI ≥ 18 to <30 kg/m² and with prediabetes is eligible for Cohort 1 or 2. This decision can be made based on the CDC definition of prediabetes of an HbA1c of 5.7% to 6.4%. If a participant has a BMI ≥ 30 to ≤ 45 kg/m² and the participant has prediabetes, the participant would be eligible for Cohorts 3 and 4 as a participant who is obese. For a participant to be included in the Cohorts 3 and 4 as a participant with diabetes (as opposed to a participant who is obese), a pre-existing diagnosis of diabetes, documented by the general practitioner or other treating physician, is required. If the participant is diagnosed with type 2 diabetes, the participant must be on treatment for type 2 diabetes; e.g. metformin, sulphonylureas, or glitazones. The diabetic participant is not eligible for Cohort 3 and 4 if not receiving treatment for type 2 diabetes at study enrolment. 	Clarification on prediabetic conditions regarding eligibility for Cohorts 1 and 2 and clarification of the requirements for a participant to be considered diabetic for assessing allocation to cohorts.

Section # and Name (page #)	Current Language	Proposed Language (New text will be bolded and deleted text will be struck through)	Rationale for Change
5.1 Inclusion Criteria (p.30)	Participant aged 55 to 75 years.	Participant aged 55 to 75 years of age at screening .	Clarification that eligible age is considered at screening.
5.1 Inclusion Criteria (p.30)	Body mass index (BMI) ≥ 18 and $\leq 30 \text{ kg/m}^2$ for healthy participants, ≥ 30 to $\leq 45 \text{ kg/m}^2$ for obese participants and ≥ 18 to $\leq 45 \text{ kg/m}^2$ for type 2 diabetic participants.	Body mass index (BMI) ≥ 18 and $\leq 30 \text{ kg/m}^2$ for healthy participants, ≥ 30 to $\leq 45 \text{ kg/m}^2$ for obese participants and ≥ 18 to $\leq 45 \text{ kg/m}^2$ for type 2 diabetic participants at screening .	Inconsistency correction, it was unclear which group a participant with a BMI of 30 should be enrolled in.
5.2 Exclusion Criteria (p.31)	NOTE: Patients with type 2 diabetes are to be recruited for Cohort 3 and Cohort 4.	NOTE: Patients with type 2 diabetes are to be recruited for Cohort 3 and Cohort 4. The autoimmune skin diseases, mild psoriasis and vitiligo, will not be considered as relevant for exclusion. Other autoimmune diseases that are not stable or are progressive/worsening (as evaluated by the investigator) should lead to exclusion.	While mild psoriasis and vitiligo are considered as autoimmune diseases, they are not considered as relevant for eligibility assessment of a participant. No additional risks for participants with mild psoriasis or vitiligo are expected.
5.2 Exclusion Criteria (p.31)	Participants who have received any vaccine within 30 days of first IMP administration, or who are planning to receive any vaccine (eg, travel vaccines) up to 30 days after each vaccination.	Participants who have received any vaccine within 30 days of first 1st IMP administration, or who are planning to receive any vaccine (eg, travel vaccines) up to 30 days after each vaccination and/or 7 days prior to 3rd administration .	Clarification on time window for participants receiving other vaccines planned around the 3 rd study dosing.
6.3.1 Participant Identification (p.34)	Participant identification numbers will be assigned sequentially to the participants who have consented to participate in the study, according to the range of participant identification numbers allocated to the study site.	Participant identification numbers will be assigned sequentially to the participants who have consented to participate in the study, according to the range of participant identification numbers allocated to the study site. Re-screening of participants will require the allocation of a new participant identification number.	Clarification regarding re-screened participants.
6.3.2 Treatment allocation to the	Allocation of the participant to treatment within a cohort	Allocation of the participant to treatment within a cohort at	Clarification to ensure consistency with actual

Section # and Name (page #)	Current Language	Proposed Language (New text will be bolded and deleted text will be struck through)	Rationale for Change
participant (p.34)	at the study site will be performed using a randomisation schedule at the site after confirming eligibility and prior to first dosing.	the study site will be performed using a randomisation schedule module of the electronic case report form (eCRF) used as Interactive Response System (IRS) at the site after confirming eligibility and prior to first 1st dosing.	setup of the randomisation system used.
6.6 Concomitant Therapy (p.36)	
Any medication or vaccine (including OTC or prescription medicines, recreational drugs, vitamins, and/or herbal supplements) that the participant is receiving at the time of enrolment or receives during the study must be recorded along with...
 
Concomitant medications (CM) may be recorded on the electronic diary (eDiary) of the participant.
	
Any medication or vaccine (including OTC or prescription medicines, recreational drugs, vitamins, and/or herbal supplements) that the participant is receiving at the time of enrolment or receives during the study must be recorded along with...
 
Concomitant medications (CM) may will be recorded on in the electronic diary (eDiary) of the participant 7 days after each vaccination.
 
NOTE: The overall collection of CMs during the study period should be done as follows (see Section 8.3.1 for AE collection details):
 
 • Day 1 – Visit 6 (Day 57): All CMs associated with an AE. • Day 58 – Day 161: Only CMs taken for MAAEs, AESIs, and SAEs, which are collected within this period. • Day 162 (7 days prior to 3rd vaccination at Visit 8) – Visit 10 (Day 197): All CMs associated with an AE. • Day 198 – Visit 12 (Day 365): Only CMs 	
Information regarding the use of recreational drugs, vitamins, and/or herbal supplements would not be required to support medical overview on participant safety nor increase the scientific value of the trial. Therefore, it is unnecessary to collect information on the use of recreational drugs, vitamins, and/or herbal supplements. Furthermore, the clarification was added that concomitant medication between 28 days post dose 2nd investigational medicinal product (IMP) administration until 3rd study IMP administration will not be required except for MAAEs, AESIs, and SAEs. The collection of unrelated concomitant medication during this period does not increase the scientific value of the study and will therefore be limited.

Section # and Name (page #)	Current Language	Proposed Language (New text will be bolded and deleted text will be struck through)	Rationale for Change
		taken for MAAEs, AESIs, and SAEs collected within this period.	
6.6.1 Permitted Concomitant Medication (p.37)	Non steroidal anti-inflammatory drugs or paracetamol at doses of ≤ 4 g/day, will be permitted for use any time during the study for the treatment of headache or other symptoms.	Non-steroidal anti-inflammatory drugs or paracetamol at doses of ≤ 4 g/day, will be permitted for use any time during the study, except within 72 hours before each vaccination , for the treatment of headache or other symptoms.	Clarification to ensure consistency with exclusion criteria.
6.6.2 Prohibited Concomitant Medications (p.37)	Any short-term medications including OTC preparations, with the exception of non-steroidal anti-inflammatory drugs or paracetamol.	Any short term medications including OTC preparations, with the exception of non-steroidal anti-inflammatory drugs or paracetamol.	Text deleted to avoid confusion. The exclusion criteria provide sufficient clarity regarding prohibited medication.
6.6.2 Prohibited Concomitant Medications (p.37)	Vaccines within 30 days of first IMP administration or planning to receive any vaccine up to 30 days after each study vaccination, with the exception of emergency vaccinations or vaccination campaigns, which will be permitted not less than 7 days before and after study vaccination.	Vaccines within 30 days of first 1st IMP administration or planning to receive any vaccine and up to 30 days after each study vaccination and 7 days prior to 3rd IMP administration , with the exception of emergency vaccinations or vaccination campaigns, which will be permitted not less than 7 days before and after study vaccination.	Clarification of prohibited use of vaccines, has been edited to specify that vaccines are prohibited within 30 days of 1 st IMP administration and up to 30 days after each study vaccination and 7 days prior to 3 rd IMP administration.
8.2.4 Electronic Diary (p.43)	For solicited systemic reactions (nausea, vomiting, diarrhoea, headache, fatigue, myalgia)	For solicited systemic reactions (chills, muscle pains/myalgia, malaise, nausea, vomiting, diarrhoea, headache, and fatigue, myalgia)	Correction of inconsistency that was present in the protocol.
8.3.1 Time Period and Frequency for Collecting AE and SAE Information (p.43)	N/A	
NOTE: The overall collection of AEs during the study period should be done as follows:
 
 Day 1 – Visit 6 (Day 57): All AEs 	Clarification regarding overall collection of AEs added.

Section # and Name (page #)	Current Language	Proposed Language (New text will be bolded and deleted text will be struck through)	Rationale for Change
		
 Day 58 – Day 161: Only MAAEs, AESIs, and SAEs Day 162 – Visit 10 (Day 197): All AEs Day 198 – Visit 12 (Day 365): Only MAAEs, AESIs, and SAEs 	
10.2 Appendix 2, Clinical Laboratory Tests, Table 6 (p.57)	White blood cell count with differential	White blood cell count with differential white blood cell (Absolute and percentages):	Clarification of white blood cell parameter
10.2 Appendix 2, Clinical Laboratory Tests, Table 6 (p.57)	Globulin	Globulin (Calculated by: total protein – albumin)	Clarification regarding how the result of the serum globulin will be obtained.
10.2 Appendix 2, Table 6: Clinical Laboratory Tests (p.57)	Human immunodeficiency virus (HIV) I and II	Human immunodeficiency virus (HIV) I and II	Local lab is not able to distinguish human immunodeficiency virus (HIV) I versus HIV II, therefore, this detail was removed.
10.3 Appendix 3: AEs and SAEs (p.59)	
Definition of Unsolicited and Solicited AE
 
An unsolicited adverse event is an adverse event that was not solicited using a participant diary and that is communicated by a participant who has signed the informed consent.
 
Unsolicited AEs include serious and non-serious AEs.
	
Timing for the collection of AEs, Definition of Unsolicited and Solicited AE
 
An unsolicited adverse event is an adverse event that was not solicited using a participant diary and that is communicated by a participant who has signed the informed consent.
 
Unsolicited AEs include serious and non-serious AEs.
 
 All AEs, AESIs, and SAEs will be collected from the 1st IMP administration. Solicited AEs are predefined events/symptoms that the participant is 	Correction made regarding timing for the collection of AEs as well as clarification of what is considered an unsolicited AE and what is considered a solicited AE.

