5.2 Exclusion Criteria

Participants are excluded from the study if any of the following criteria apply:

1. Participants who have received a GBS vaccine previously.
2. Participants with history or presence of significant (as evaluated by the investigator) cardiovascular disease, pulmonary, hepatic, gallbladder or biliary tract, renal, haematological, gastrointestinal, endocrine, immunologic, dermatological, neurological, psychiatric, autoimmune disease, or current infection.

NOTE: Patients with type 2 diabetes are to be recruited for Cohort 3 and Cohort 4. The autoimmune skin diseases, mild psoriasis and vitiligo, will not be considered as relevant for exclusion.

Other autoimmune diseases that are not stable or are progressive/worsening (as evaluated by the investigator) should lead to exclusion.

3. Laboratory values at screening which are deemed by the investigator to be clinically significantly abnormal.
4. Current or history of drug or alcohol abuse per investigator judgement.
5. Positive for human immunodeficiency virus (HIV), hepatitis B, or hepatitis C.
6. Participants currently participating in a clinical trial.
7. Participants receiving an investigational drug, vaccine or device during the 90 days preceding the initial dose in this study.
8. Any significant illness during the 4 weeks preceding the vaccination visit, per investigator judgement.
9. Participants with a history of severe allergic reactions after previous vaccination.
10. Participants who have received any vaccine within 30 days of 1st IMP administration, or who are planning to receive any vaccine (eg, travel vaccines) up to 30 days after each vaccination and/or 7 days prior to 3rd administration.

NOTE: Exceptions could be made for emergency vaccinations (eg, tetanus) or vaccination campaigns (eg, SARS, CoV-2 or influenza) which will be permitted not less than 7 days before or after study vaccination.

11. Participants receiving immunosuppressive therapy or immunoglobulins in the 6 months prior to screening.
12. Participants within a 7-day period after an acute infection in the 7 days preceding vaccination, as per investigator judgement, or with fever (oral temperature >37.9°C) in the 72 hours preceding vaccination.
13. Participants who have received antipyretics/analgesics treatment within 72-hours prior to dosing.
14. Participants on chronic medications that are likely to affect the assessments specified in the protocol (eg, anticoagulant therapy, systemic steroids).

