8.3.1 Time Period and Frequency for Collecting AE and SAE Information

All AEs and SAEs will be collected from the 1st IMP administration until the follow-up visit at the time points specified in the SoA (Section [1.3](#)).

NOTE: The overall collection of AEs during the study period should be done as follows:

- *Day 1 – Visit 6 (Day 57): All AEs*
- *Day 58 – Day 161: Only MAAEs, AESIs, and SAEs*
- *Day 162 – Visit 10 (Day 197): All AEs*
- *Day 198 – Visit 12 (Day 365): Only MAAEs, AESIs, and SAEs*

Medical occurrences that begin before the start of IMP administration but after obtaining informed consent will be recorded as MH, not as AEs.

All SAEs will be recorded and reported to the Sponsor or designee immediately and under no circumstance should this exceed 24 hours of the investigator's awareness of the event, as indicated in Section 10.3. The investigator will submit any updated SAE data to the Sponsor or designee within 24 hours of their awareness of the updated information.

Investigators are not obligated to actively seek information on AEs or SAEs after conclusion of the study participation. However, if the investigator learns of any SAE, including a death, at any time after a participant has been discharged from the study, and he/she considers the event/cause of death to be reasonably related to the investigational product or study participation, the investigator must promptly notify the Sponsor or designee.

The method of recording, evaluating, and assessing causality of AE and SAE and the procedures for completing and transmitting safety reports are provided in Section 10.3.

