8.3.4 Regulatory Reporting Requirements for SAEs

Prompt notification by the investigator to the Sponsor or designee of an SAE is essential so that legal obligations and ethical responsibilities toward the safety of participants and the safety of an IMP under clinical investigation are met.

The Sponsor has a legal responsibility to notify both the local regulatory authority and other regulatory agencies about the safety of an IMP under clinical investigation. The Sponsor will comply with country-specific regulatory requirements relating to safety reporting to the regulatory authority, EU Eudravigilance Database (as applicable), IRBs/IECs, and Investigators.

An investigator who receives an investigator safety report describing an SAE or other specific safety information (eg, summary or listing of SAEs) from the Sponsor will review and then file it along with the IB and will notify the IRB/IEC, if appropriate according to local requirements.

Investigator safety reports must be prepared for SUSARs according to local regulatory requirements and Sponsor policy and forwarded to Investigators as necessary.

8.3.5 **Solicited Adverse Events**

Local and systemic predefined solicited AEs for reactogenicity assessment will be collected by the participant in a solicited AE eDiary for 7 days following each study vaccination. The set of solicited AEs associated with reactogenicity are presented in Table 4.

Table 4 Reactogenicity Assessment: List of solicited adverse events

Local	Systemic
Pain at the site of injection	Fever (>100°F [>37.9°C]) ^a
Erythema/redness at the site of injection	Chills
Tenderness	Muscle pains
Induration/swelling at the site of injection	Fatigue
Itching	Headache
	Malaise
	Nausea
	Vomiting

^a Fever measured orally. Investigators who consider a temperature lower than this cutoff as a fever or a ‘fever’ reported by participants without documentation by a thermometer should record the event as ‘elevated body temperature’.

8.3.6 **Adverse Events of Special Interest and Medically Attended Adverse Events**

Adverse events will be monitored throughout the study to identify any event of interest that may indicate a trend or risk to participants. The following are considered adverse events of special interest (AESI):

- Development of autoimmune diseases
- GBS infections
- Symptomatic GBS urinary tract infections

A MAAE is an AE that leads to an unscheduled visit to a health care provider.

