
• Any abnormal laboratory test results (haematology, clinical chemistry, or urinalysis) or other safety assessments (eg, ECG, radiological scans, vital signs measurements), including those that worsen from baseline, considered clinically significant in the medical and scientific judgement of the investigator (ie, not related to progression of underlying disease).• Exacerbation of a chronic or intermittent pre-existing condition including either an increase in frequency and/or intensity of the condition.

- New condition detected or diagnosed after IMP administration even though it may have been present before the start of the study.

Events NOT Meeting the AE Definition

- Any clinically significant abnormal laboratory findings or other abnormal safety assessments that are associated with the underlying disease, unless judged by the investigator to be more severe than expected for the participant's condition.
- The disease/disorder being studied or expected progression, signs, or symptoms of the disease/disorder being studied, unless more severe than expected for the participant's condition.
- Medical or surgical procedure (eg, endoscopy, appendectomy): the condition that leads to the procedure is the AE.
- An elective surgery/procedure scheduled to occur during a study will not be considered an AE if the surgery/procedure is being performed for a pre-existing condition and the surgery/procedure has been pre planned prior to study entry. However, if the pre-existing condition deteriorates unexpectedly during the study (eg, surgery performed earlier than planned), then the deterioration of the condition for which the elective surgery/procedure is being done will be considered an AE.
- Anticipated day-to-day fluctuations of pre-existing disease(s) or condition(s) present or detected at the start of the study that do not worsen.

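### Worsening of pre-existing autoimmune disease is not named as an AESI, so in the restricted collection periods a non-serious flare with no unscheduled visit is not collected

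*Protocol*

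**What the plan says.** **Who can enter.** Exclusion 2 (Protocol 5.2) removes people with a history or presence of autoimmune disease that the investigator considers significant. The NOTE beneath it adds "mild psoriasis and vitiligo, will not be considered as relevant for exclusion. Other autoimmune diseases that are not stable or are progressive/worsening", the latter being excluded on the investigator's evaluation.

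**What counts as an AESI.** Protocol 8.3.6 lists three items. Two concern GBS infection. The only autoimmune item is "Development of autoimmune diseases". The SAP reports AESIs but does not define them.

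**What counts as an AE.** Appendix 3 (Protocol 10.3.1) includes "Exacerbation of a chronic or intermittent pre-existing condition including either an increase in frequency and/or intensity of the condition". A flare is therefore an AE.

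**What is collected, and when.** The NOTE in Protocol 8.3.1 begins "Day 1 – Visit 6 (Day 57): All AEs" and continues "Day 58 – Day 161: Only MAAEs, AESIs, and SAEs". Full collection resumes from Day 162 to Visit 10 (Day 197), and the restriction returns from Day 198 to Visit 12 (Day 365). Footnote j of the Schedule of Activities also restricts the late periods to these three categories. Under 8.3.6 a MAAE requires an unscheduled visit to a health care provider.

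**Where AESIs are reported.** AESIs within 28 days of each dose belong to the primary endpoints (SAP 3.1). AESIs from Day 197 to Day 365 belong to the secondary safety endpoints (SAP 3.3). SAP 17.1.1 plans summaries that include AESIs for Day 57 to Day 168 and from 28 days after the third dose to Day 365.

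**The concern.** The eligibility text allows for people who already have an autoimmune condition, while the AESI definition speaks only of one that develops. In someone with existing disease, an autoimmune effect of the vaccine could appear as worsening rather than as a new diagnosis. The definition does not name that form of the event.

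During full collection this affects only how the event is labelled. During restricted collection the label decides whether the event is collected at all, unless it is serious or medically attended. If the late-period AESI summary shows no autoimmune events, a reader cannot tell whether there were no flares or whether flares fell outside the collection rule. Medical history is only listed (SAP 13), so no planned table shows how many participants could have flared.

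**Working it through.** The plan states no figure on this point. The check is a day count and a classification.

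**Step 1. Length of each collection window** (Protocol 8.3.1; last day − first day + 1)

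- All AEs: 57 − 1 + 1 = 57 and 197 − 162 + 1 = 36; total 93 days.
- MAAEs, AESIs and SAEs only: 161 − 58 + 1 = 104 and 365 − 198 + 1 = 168; total 272 days.
- Check: 93 + 272 = 365.
- Shares: 93/365 = 25.5% full, 272/365 = 74.5% restricted.

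Visit 12 has a window of ±14 days:

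- Day 351: 104 + (351 − 197) = 258; 258/351 = 73.5%.
- Day 379: 104 + (379 − 197) = 286; 286/379 = 75.5%.

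**Step 2. Are the 28-day post-dose periods fully covered?** Nominal dose days are 1, 29 and 169.

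- 1 + 28 = 29, inside Days 1–57.
- 29 + 28 = 57, inside Days 1–57.
- 169 + 28 = 197, inside Days 162–197.

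All three lie inside full collection on nominal dates.

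**Step 3. What happens to a flare of pre-existing disease**, reading the AESI item as new onset and applying the 8.3.1 NOTE:

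| Flare | Days 1–57 and 162–197 | Days 58–161 and 198–365 |
|---|---|---|
| Serious | Collected as SAE | Collected as SAE |
| Non-serious, unscheduled visit | Collected as AE and MAAE | Collected as MAAE |
| Non-serious, no unscheduled visit | Collected as unsolicited AE, no AESI label | Not collected |

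Within 28 days of a dose, an unsolicited AE is tabulated by system organ class and preferred term with an exact 95% CI (SAP 17.1). The flare is therefore visible there, though absent from the AESI table. The gap is the bottom-right cell.

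**Step 4. Does the SAP close the gap?** Its treatment-emergent definition (SAP 17.1) includes AEs that worsen, but it can act only on events that were recorded.

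**Step 5. Effect of naming worsening as an AESI.** A flare in the bottom row becomes collectable on 365 of 365 nominal days instead of 93.

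**The case against.** The case against is substantial, and much of it stands.

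- **Eligibility is narrower than the NOTE alone suggests.** A reader might infer that only unstable autoimmune disease is excluded. The documents do not support that: exclusion 2 removes significant disease, exclusion 11 removes recent immunosuppressive therapy or immunoglobulins, and exclusion 14 removes chronic medication likely to affect the assessments. Entry of other stable disease is an implication of the NOTE. For mild psoriasis and vitiligo, the amendment rationale says no additional risk is expected. That is a fair basis for admitting them, but the trial should be able to check it.
- **The primary endpoint loses no event.** A reader might infer that flares drop out of the primary safety analysis. On nominal dates they do not; only the AESI classification is missing.
- **Most clinically important flares are captured.** It would be wrong to infer that flares in general go unrecorded for most of the study. Serious or medically attended flares are collected throughout.
- **Other protocol text points towards collection.** The opening sentence of 8.3.1 has all AEs collected until the follow-up visit. Appendix 3 asks participants to report unattended events that concern them, has other unattended AEs collected by interview at the next visit, and describes medical attendance more broadly than 8.3.6. This is a real conflict. The NOTE and footnote j are the specific rules, and a site following them would not collect the event.
- **The AESI wording is undefined.** An investigator might read it to include a flare. Inconsistent readings would themselves be a reason to define it.

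A reader might also want a count of missed flares or a shifted confidence limit. The documents support neither. They give no number of participants with autoimmune disease. The SAP reports vaccine groups separately by population and dose (SAP 7.2). Its exact intervals for AESIs belong to the 28-day tables, where flares are recorded, while the late-period summaries in SAP 17.1.1 specify only number and percentage.

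**Conclusion.** The point holds in limited form. Within 28 days of a dose, a flare of pre-existing autoimmune disease loses only its AESI label. On 272 of 365 nominal days (74.5%; 73.5% to 75.5% across the Visit 12 window), a flare that is non-serious and leads to no unscheduled visit is not collected under the 8.3.1 NOTE. The long-term AESI summary then cannot separate no flares from flares not collected.

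This rests on four assumptions: the AESI item means new onset, as its plain wording suggests; the NOTE and footnote j prevail over the general sentence in 8.3.1 and the interview text in Appendix 3; nominal visit days apply; and at least some participants have admissible autoimmune disease. The number affected cannot be derived from the documents. The change is worth making because it is cheap and improves the long-term safety data. The point does not undermine the primary analysis.

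**What to change.** 1. In Protocol 8.3.6, reword the first AESI as: *New onset or worsening (exacerbation, as in Appendix 3) of an autoimmune disease.* Tying it to Appendix 3 supplies a threshold, because that appendix already treats expected day-to-day fluctuation without worsening as not an AE.
2. In SAP 17.1 and 17.1.1, report new onset and worsening in separate rows, so that new-onset events stay visible.
3. Reconcile the opening sentence of Protocol 8.3.1 and the Appendix 3 interview text with the collection-window NOTE, so that sites have one rule for the late periods.

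No visit or test is added. The cost is a protocol amendment with the ethics approval that Protocol 10.1.1 requires, split rows in the AESI tables, and possibly a slightly higher AESI count. If data collection has closed, apply the split to the AEs already recorded and state the late-period gap as a limitation in the study report.
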